## Appendix O Laboratory procedures for Part B (no leukapheresis and no lymph node FNA)

				Visit:	1	2 ¹²	3	4	5	6	7	8	9	10	11	12	13	14	15	16	
				Day:	-	D0	D1	D3	D7	D14	D56	D63	D70	D77	D168	D175	D182	D224	D364	D546	
				Week:	Screening	W0	D1		W1	W2	W8	W9	W10	W11	W24	W25	W26	W32	W52	W78	
				Month:	visit ⁴	MO	·	-	M0.25	M0.5	M2	M2.25	M2.5	M2.75	M6	M6.25	M6.5	M8	M12	M18	
		Assay		(vol.		VAC1	l	-	W.C.EC	1110.0	VAC2	- IVIE.EU			VAC3		1110.0				
Procedure	Ship to ¹	location ²	Tube type ³	capacity)		.,									17100						Total
BLOOD COLLECTION			71		1	3				8	1						5				
Screening/Diagnostic																					
HIV screening test	Local lab	Local lab	SST	5mL	5	T -	I –	I –	_		_	T -	T -			T -	T -		_	_	5
HBs Ag/ anti-HCV	Local lab	Local lab	SST	5mL	5	 	 	 	l –	_	_	 	T -		 	 	_		_	_	5
HIV diagnostics ⁸	UW-VSL	UW-VSL	EDTA	10mL	_	_	l –	T —	_	_	_	T -	10		10	l –	 		10	20	50
Safety labs			·	3	·	·			·	&	 	4		***************************************		 		······		·····	
CBC/ Diff/ Platelets	Local lab	Local lab	EDTA	5mL	5	T —	I —	T —	Ι –	5	T —	T —	5	T	T —	I –	5		5		25
Chemistry panel ⁵	Local lab	Local lab	SST	5mL	5	T -	_	_	_	5	_	_	5		_		5		5	_	25
Immunogenicity assays				£					•				-			•					
Cellular assays	*****************************	******************************	******************************	***************************************	***********************															***************************************	***************************************
Tfh/pTfh phenotyping	CSR	HVTN Labs	ACD	8.5mL	T -	25.5	Ι –	T —	25.5	T -	Ι –	25.5				25.5	T -		_	25.5	128
Ag-specific B-cell phenotyping	CSR	HVTN Labs	ACD	8.5mL	 	17	_	 	-	34	_	-	34		_	-	34		34	17	170
Ag-specific Plasmablast phenotyping	CSR	HVTN Labs	ACD	8.5mL	T -	_	 	_	17	_	_	34	 		_	34	_		_	34	119
B-cell repertoire analysis	CSR	HVTN Labs	ACD	8.5mL	<del>                                     </del>	34	 	 	 	_	 	<del>                                     </del>	34		l –	<del>                                     </del>	34		34	34	170
ICS	CSR	HVTN Labs	ACD	8.5mL	<del>                                     </del>		<del> </del>	<del> </del>	<del> </del>	_		<del>                                     </del>	34	 	T -		34		34	34	136
Humoral assays								-	-	8											
Binding Ab assay	CSR	HVTN Labs	SST	8.5mL	T —	8.5	T _	 	T -	T -	T _	_	8.5		_	 	8.5		8.5	8.5	43
Neutralizing Ab assay	CSR	HVTN Labs	SST	8.5mL	l –	8.5	<del>                                     </del>	_	—		_	 	8.5		l –	t –	8.5		8.5	8.5	43
Fc-mediated Ab functions ⁹	CSR	HVTN Labs	SST	8.5mL	<del> </del>	V		_	_		_	_	V		_	 	V		V	V	
Innate immunity and inflammation assays	3	1	1		1	. ,	1	 	1	1	1					 	. ,				
Phenotyping	CSR	HVTN Labs	ACD	8.5mL	T -	8.5	8.5	8.5	8.5	_	8.5	T —	T	T	8.5	I –	Ι _	T		_	51
RNA gene expression	CSR	HVTN Labs	Tempus	3mL	 	3	3	3	3	_	3	<del>                                     </del>	3		3	<del>                                     </del>	3			_	24
Serum cytokines/chemokines	CSR	HVTN Labs	SST	5mL	<del> </del>	5	5	5	5		5	<del>                                     </del>	<del>                                     </del>		5	<del>                                     </del>	 				30
STORAGE	-								-	8		-									
PBMC	CSR	T -	ACD	8.5mL	Т —	34	T —	T -	17	68	T =	34	68		_	68	153		102	42.5	587
Serum ¹⁶	CSR	1 –	SST	8.5mL	T —	25.5	8.5	8.5	8.5	25.5	_	T -	17		 	l –	25.5		17	17	153
Visit total					20	170	25	25	85	138	17	94	227		27	128	311		258	241	1762
56-Day total ¹⁰		1			20	190	215	240	324	462	478	332	475		27	154	465		258	241	
URINE COLLECTION		1	1	1		1	1		-	1	1										
Urine dipstick ⁶	Local lab	Local lab			X	T —	Ι –	T _	T -	Х	_	Τ —	T —		_	T —	Х		_	_	
Pregnancytest ⁷	Local lab	Local lab			X	X	T	_			Х	<del> </del>	 	 	X	 	X ¹¹	·	Х	X ¹¹	
Chlamydia/Gonorrhea ¹³	Local lab	Local lab			<del> </del>	X		_	_	_	_	_	 		_	_	X		_		
RECTAL SWAB COLLECTION				š			£	·	4				 				 				
Chlamydia/Gonorrhea ¹³	Local lab	Local lab			T —	X	T —	T —	T -	T -	T -	T -	T —			T –	Х		_		
CERVICAL/VAGINAL SWAB COLLECTION				\			·····	·		å	·	·	J	d	<del></del>	 					
Chlamydia/Gonorrhea ¹³	Local lab	Local lab			T —	X	_	_	T -	_	_	T -	T -		_	I –	Х		_	_	
Trichomonas vaginalis 14	Local lab	Local lab			<del>                                     </del>	 	<del>                                     </del>		 			<del>                                     </del>	<del>                                     </del>		 	<del>                                     </del>			_		
Bacterial vaginosis ¹⁵	Local lab	Local lab			T -	 	 	<del> </del>		_		 	 	·	 	<del>                                     </del>	<del></del>			_	T
Yeast ¹⁵	Local lab	Local lab			1 –	 	 	 	1 –	_	 	<del>                                     </del>	<del>                                     </del>	 	1 –	<del>                                     </del>	l –	ļ			
OTHER COLLECTIONS (OPTIONAL)	-1		1		1	1				8	-	-	-				 				-
Bone marrow aspirate	CSR	HVTN Labs			T —	_	T	I –	T —		T —	Τ –	T —		_	I –	T -		_	Х	
MUCOSAL SECRETION COLLECTION (OPTIC	-4		<del>4</del>	4	4	·		 	***************************************	9	1		1			1	*			·	I
Cervicovaginal secretions	CSR	HVTN Labs			Ι –	X	_	 	T -	_	 	T		******************	T —	 	Х		_		
Rectal secretions	CSR	HVTN Labs			<del> </del>	X	 	<del> </del>	<del> </del>		_	 	 		_	<del>                                     </del>	Х		_	_	
MUCOSAL BIOPSY COLLECTION (OPTIONAL		,	*			1										1				Total E	Biopsies
Vaginal biopsies	CSR	HVTN Labs	T		T –	5	_	——————————————————————————————————————	T -	_	_	T				_	5		_		10
Colorectal biopsies	CSR	HVTN Labs			<del> </del>	5	 		_	_	_	T -	_		_		5		_		10
	,	,	-	-	-		,			*					2						

¹ CSR = Central Specimen Repository; UW-VSL = University of Washington Virology Specialty Laboratory (Seattle, Washington, USA).

² HVTN Laboratories include: Fred Hutchinson Cancer Research Center (Seattle, Washington, USA); Duke University Medical Center (Durham, North Carolina, USA).

³ Local labs may assign appropriate alternative tube types for locally performed tests.

⁴ Screening may occur over the course of several contacts/visits up to and including day 0 prior to vaccination.

- ⁵ Chemistry panels are defined in Section 9.2 (pre-enrollment procedures) and Section 9.4 (follow-up visits).
- ⁶ And microscopy if needed.
- ⁷ For participants assigned female sex at birth. Pregnancy test may be performed on blood specimens. Persons who are NOT of reproductive potential due to having undergone total hysterectomy or bilateral oophorectomy (verified by medical records), are not required to undergo pregnancy testing.
- ⁸ At an early termination visit for a withdrawn or terminated participant who is not HIV-infected (see Section 9.12), blood should be drawn for HIV diagnostic testing, as shown for visit 16 above. If a participant has a confirmed diagnosis of HIV infection, do not collect blood for HIV diagnostic testing (see Section 9.14).
- ⁹ Fc-mediated Ab functions may include FcR binding assay, ADCC, ADNP ADCP, and complement assay.
- ¹⁰ The 56-day total blood volume does not include up to 16.5 mL blood collected for a reaction (see Section 9.10.1); however, the 56-day limit is not exceeded at any visit by this possible collection.
- ¹¹ Pregnancy testing at indicated visit is only required of participants who were assigned female sex at birth and are providing optional procedure samples (bone marrow aspirate and rectal or vaginal mucosal secretion or biopsy). See Section 9.5 for the timing of the pregnancy test in order to meet eligibility requirements for the optional procedures.
- ¹² Specimens indicated for Day 0 may be obtained within the 14 days prior to vaccination, except for a pregnancy test which must be performed on urine or blood specimens within 24 hours of vaccination with negative results received prior to vaccination.
- ¹³ Chlamydia/gonorrhea testing will only be performed for participants providing biopsy samples. In males, chlamydia/gonorrhea testing will be done on both rectal swabs and urine. In females, chlamydia/gonorrhea testing will be done on rectal swabs and on urine or vaginal swabs.
- ¹⁴ Trichomonas testing will be done with cervical/vaginal swabs or urine and will only be performed when clinically indicated for participants who agree to provide cervicovaginal secretion or vaginal biopsy samples.
- ¹⁵ Cervical/vaginal swabs for yeast and bacterial vaginosis testing will only be performed when clinically indicated for participants who agree to provide cervicovaginal secretion or vaginal biopsy samples.
- ¹⁶ Antibody avidity, peptide microarray, metabolomic profiles, and proteomics assays may be done with serum collected for storage.
- y = SST blood collected for the Binding Ab and Neutralizing Ab assays will also cover specimen needs for the Fc-mediated Ab function assays; no separate blood draw is needed.

## Appendix P Laboratory procedures for Part B (no optional procedures) and Part C

				Visit:	1	2 ¹¹	3	4	5	6	7	8	9	10	11	12	13	14	15	16	Ī
				Day:		D0	D1	D3	D7	D14	D56	D63	D70	D77	D168	D175	D182	D224	D364	D546	
				Week:	Screening	WO			W1	W2	W8	W9	W10	W11	W24	W25	W26	W32	W52	W78	
				Month:	visit ⁴	MO			M0.25	M0.5	M2	M2.25	M2.5	M2.75	M6	M6.25	M6.5	M8	M12	M18	
		Assay		Tube size		VAC1					VAC2				VAC3						1
Procedure	Ship to ¹	location ²	Tube type ³	(vol.																	Total
BLOOD COLLECTION																					
Screening/Diagnostic																					
HIV screening test	Local lab	Local lab	SST	5mL	5	_	_	_	_	_	_	_	_		_	_	_		_	_	5
HBsAg/ anti-HCV	Local lab	Local lab	SST	5mL	5	_	_	T —	_	_	_	_	_		_						5
HIV diagnostics ⁸	UW-VSL	UW-VSL	EDTA	10mL	_	_	_		T —	_	_	_	10		10	T —	_		10	20	50
Safety labs																					
CBC/ Diff/ Platelets	Local lab	Local lab	EDTA	5mL	5	I –	_	T —	I –	5		_	5		I –	T -	5		5	I –	25
Chemistry panel ⁵	Local lab	Local lab	SST	5mL	5	_	l –	T -	T -	5	_	_	5		I –	T —	5		5	 	25
Immunogenicity assays		***************************************					 		***************************************					~~~~				***************************************		***************************************	
Cellular assays						***************************************		0-00-000-000-000-000-00	0*****************************	***********************		POODPOODPOODPOODPOODPOODP		•••••	0-000-000-000-000-000-00		***************************************	*******************			2000000000000000000000
Tfh/pTfh phenotyping	CSR	HVTN Labs	ACD	8.5mL	_	25.5	_	I –	25.5	_	_	25.5	_		—	25.5	T —		_	25.5	128
Ag-specific B-cell phenotyping	CSR	HVTN Labs	ACD	8.5mL	_	17	_	 		34			34		—		34		34	17	170
Ag-specific Plasmablast phenotyping	CSR	HVTN Labs	ACD	8.5mL	_	_	_	l —	17	_	_	34	_		 	34	 		_	34	119
B-cell repertoire analysis	CSR	HVTN Labs	ACD	8.5mL	_	34	l –	T	T -	_	_		34			T	34		34	34	170
ICS	CSR	HVTN Labs	ACD	8.5mL	_	 	l —	 	 	_	 	_	34		l –	 	34		34	34	136
Humoral assays						······		······						•				•			
Binding Ab assay	CSR	HVTN Labs	SST	8.5mL		8.5	I –	T -	T —	_			8.5		_		8.5		8.5	8.5	43
Neutralizing Ab assay	CSR	HVTN Labs	SST	8.5mL	_	8.5	_	 		_			8.5		_	T -	8.5	1	8.5	8.5	43
Fc-mediated Ab functions 9	CSR	HVTN Labs	SST	8.5mL	_	У		1 —	T -	—	 	_	У		 		У		У	У	
Innate immunity and inflammation assays	 	··········					A				***************************************	200000000000000000000000000000000000000						***************************************	8		
Phenotyping	CSR	HVTN Labs	ACD	8.5mL	_	8.5	8.5	8.5	8.5	_	8.5	_	_		8.5	T —	T -		_	I –	51
RNA gene expression	CSR	HVTN Labs	Tempus	3mL	_	3	3	3	3	_	3	_	3		3		3		_	_	24
Serum cytokines/chemokines	CSR	HVTN Labs	SST	5mL	_	5	5	5	5	_	5	_	_		5	T	T —		_	l –	30
STORAGE			 	 	O		····			0		***************************************		***************************************	***************************************		***************************************	*****************		***************************************	
PBMC	CSR	_	ACD	8.5mL	_	34	l –	T -	17	68	_	34	68		I –	68	153	T	102	42.5	587
Serum ¹²	CSR		SST	8.5mL	_	25.5	8.5	8.5	8.5	25.5	_	_	17		_	_	25.5		17	17	153
Visit total					20	170	25	25	85	138	17	94	227		27	128	311		258	241	1762
56-Day total ¹⁰	f				20	190	215	240	324	462	478	332	475		27	154	465		258	241	1
URINE COLLECTION																					
Urine dipstick ⁶	Local lab	Local lab		,,,,,,,,,,,,,,,,,,,,,,,,,,,,,,,,,,,,,,,	X	_	—	T -	T -	Х	_	_			I –	T -	X		I –	I –	T
Pregnancy test ⁷	Local lab	Local lab			X	X		<del> </del>	T =	_	X				X	T _	 		X	 	1

¹ CSR = Central Specimen Repository; UW-VSL = University of Washington Virology Specialty Laboratory (Seattle, Washington, USA).

² HVTN Laboratories include: Fred Hutchinson Cancer Research Center (Seattle, Washington, USA); Duke University Medical Center (Durham, North Carolina, USA).

³ Local labs may assign appropriate alternative tube types for locally performed tests.

⁴ Screening may occur over the course of several contacts/visits up to and including day 0 prior to vaccination.

⁵ Chemistry panels are defined in Section 9.2 (pre-enrollment procedures) and Section 9.4 (follow-up visits).

⁶ And microscopy if needed.

⁷ For participants assigned female sex at birth. Pregnancy test may be performed on blood specimens. Persons who are NOT of reproductive potential due to having undergone total hysterectomy or bilateral oophorectomy (verified by medical records), are not required to undergo pregnancy testing

⁸ At an early termination visit for a withdrawn or terminated participant who is not HIV-infected (see Section 9.12), blood should be drawn for HIV diagnostic testing, as shown for visit 16 above. If a participant has a confirmed diagnosis of HIV infection, do not collect blood for HIV diagnostic testing (see Section 9.14).

⁹ Fc-mediated Ab functions may include FcR binding assay, ADCC, ADNP ADCP, and complement assay.

¹⁰ The 56-day total blood volume does not include up to 16.5 mL blood collected for a reaction (see Section 9.10.1); however, the 56-day limit is not exceeded at any visit by this possible collection.

¹¹ Specimens indicated for Day 0 may be obtained within the 14 days prior to vaccination, except for a pregnancy test which must be performed on urine or blood specimens within 24 hours of vaccination with negative results received prior to vaccination.

¹² Antibody avidity, peptide microarray, metabolomic profiles, and proteomics assays may be done with serum collected for storage.

y = SST blood collected for the Binding Ab and Neutralizing Ab assays will also cover specimen needs for the Fc-mediated Ab function assays; no separate blood draw is needed.

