To evaluate innate immune responses and baseline predictors, compare the innate immune responses elicited by BG505 SOSIP.664 gp140 with various adjuvants (CpG 1018 + Alum, 3M-052-AF + Alum, GLA-LSQ, or Alum) after the first vaccination, and correlate with adaptive immune responses

Secondary endpoints 5:

Alterations in blood leukocyte populations during the innate response (day 1, 3 and 7) relative to prevaccine levels (day 0)

Alterations in RNAseq expression of leukocyte and/or immune cells (lymphocyte populations, natural killer (NK) cells, dendritic cell (DC) subsets, monocytes subsets, and granulocytes) (days 1, 3, and 7) relative to prevaccine levels (day 0)

Alterations of concentrations of immune cytokines and chemokines in serum samples postvaccination (days 1, 3, 7) relative to prevaccine levels (day 0)

Secondary objective 6:

To characterize systemic inflammatory markers among participants with moderate to severe reactogenicity after any vaccination

Secondary endpoint 6

Blood cell subpopulation dynamics by multiparameter flow cytometry, gene expression alterations by RNAseq/transcripts and soluble cytokine/inflammatory mediator alterations comparing day of last vaccination and day of visit for moderate to severe reactogenicity

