Percent HIV Env-specific cytokine-expressing CD4+ T cells in blood by intracellular cytokine staining (ICS) multiparameter flow cytometry and polyfunctional subset analysis 2 weeks after the second vaccination and 2 weeks, 6 months, and 12 months after the third vaccination

Secondary objective 5:

To evaluate innate immune responses and baseline predictors, compare the innate immune responses elicited by BG505 SOSIP.664 gp140 adjuvanted with 3 mcg of 3M-052-AF+Alum, and by Trimer 4571 adjuvanted with 5 mcg of 3M-052-AF+Alum after the first vaccination, and correlate with adaptive immune responses

Secondary endpoints 5:

Alterations in blood leukocyte populations during the innate response (day 1, 3 and 7) relative to prevaccine levels (day 0)

Alterations in RNAseq expression of leukocyte and/or immune cells (lymphocyte populations, natural killer (NK) cells, dendritic cell (DC) subsets, monocytes subsets, and granulocytes) (days 1, 3, and 7) relative to prevaccine levels (day 0)

Alterations of concentrations of immune cytokines and chemokines in serum samples postvaccination (days 1, 3, 7) relative to prevaccine levels (day 0)

Secondary objective 6:

To characterize systemic inflammatory markers among participants with moderate to severe reactogenicity after any vaccination

Secondary endpoint 6

Blood cell subpopulation dynamics by multiparameter flow cytometry, gene expression alterations by RNAseq/transcripts and soluble cytokine/inflammatory mediator alterations comparing day of last vaccination and day of visit for moderate to severe reactogenicity

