response distributions. Lachenbruch's test statistic equals the square of a binomial Z-statistic for comparing the response rates plus the square of a Wilcoxon statistic for comparing the response distributions in the subgroup of responders. A permutation procedure is used to obtain a 2-sided p-value. For estimation, differences in response rates between arms will be estimated using the methods described above, and in the subgroup of positive responders, differences in location parameters between arms will be estimated using the methods described above.

More sophisticated analyses employing repeated measures methodology (for example, linear mixed models or marginal mean models fit by generalized estimating equations) will be utilized to incorporate immune responses over several timepoints and to test for differences over time and differences in trajectories across treatment arms. For example, repeated measures analyses will be conducted to evaluate trajectories in innate immune responses over Days 1, 3, 7 relative to responses measured at Day 0. However, inference from such analyses would be limited by the small sample size of this study. All statistical tests will be 2-sided and will be considered statistically significant if $p \le 0.05$.

Based upon previous HVTN trials, missing 10% of immunogenicity results for a specific assay is common due to study participants terminating from the study early, problems in shipping specimens, or low cell viability of processed PBMCs. To achieve unbiased statistical estimation and inferences with standard methods applied in a complete-case manner (only including participants with observed data in the analysis), missing data need to be missing completely at random (MCAR). Following the most commonly used definition, MCAR assumes that the probability of an observation being missing does not depend on any participant characteristics (observed or unobserved). When missing data are minimal (specifically if no more than 20% of participants are missing any values), then standard complete-case methods will be used, because violations of the MCAR assumption will have little impact on the estimates and hypothesis tests.

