- 12. Any vaccines that are not live attenuated vaccines and were received within 14 days prior to first vaccination or scheduled for 14 days after injection (eg, tetanus, pneumococcal, hepatitis virus A or B); replication incompetent vaccines such as the Jynneos monkeypox vaccine are not considered to be live vaccines
- 13. Previous receipt of HEPLISAV, Shingrix, or RTS,S/AS01B/Mosquirix vaccine received within 30 days prior to first vaccination or scheduled for 30 days after injection.
- **14. Allergy treatment with antigen injections** within 30 days before first vaccination or that are scheduled within 14 days after first vaccination

Immune System

- 15. Immunosuppressive medications received within 168 days before first vaccination (Not exclusionary: [1] corticosteroid nasal spray; [2] inhaled corticosteroids; [3] topical corticosteroids for mild, uncomplicated dermatologic condition; or [4] a single course of oral/parenteral prednisone or equivalent at doses ≤ 60 mg/day and length of therapy < 11 days with completion at least 30 days prior to enrollment)
- 16. Serious adverse reactions to vaccines or to vaccine components, including history of anaphylaxis and related symptoms such as hives, respiratory difficulty, angioedema, and/or abdominal pain. (Not excluded from participation: a volunteer who had a non-anaphylactic adverse reaction to pertussis vaccine as a child.)

- 17. **Immunoglobulin** received within 60 days before first vaccination (for mAb see criterion 8 above)
- 18. Autoimmune disease, current or history
- 19. **AESIs:** Volunteers who currently have, or have a history of, any condition that could be considered an AESI for the product(s) administered in this protocol (representative examples are listed in Appendix V)

20. Immunodeficiency

Clinically significant medical conditions

- 21. Clinically significant medical condition, physical examination findings, clinically significant abnormal laboratory results, or past medical history with clinically significant implications for current health. A clinically significant condition or process includes but is not limited to:
 - A process that would affect the immune response,
 - A process that would require medication that affects the immune response,
 - Any contraindication to repeated injections or blood draws,
 - A condition that requires active medical intervention or monitoring to avert grave danger to the volunteer's health or well-being during the study period,

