10.3 Primary immunogenicity timepoint

The primary immunogenicity timepoints in this study occur 2 weeks after the last vaccination for groups receiving 2 vaccinations and 1 and 2 weeks after the second and third vaccinations for the groups receiving 3 vaccinations. For the

group receiving 3 vaccinations, primary timepoints for innate immunity and inflammation assays are baseline, and days 1, 3, and 7 post first vaccination.

Endpoint assays for humoral and cellular responses are performed on specimens collected from participants at the primary immunogenicity timepoint and may be performed on samples collected at baseline. Depending on the initial results, assays for humoral, cellular, innate immunity, and inflammatory responses may be performed on samples collected from participants at other timepoints; the schedules are shown in Appendix J, Appendix K, Appendix L, Appendix M, Appendix N, Appendix O, and Appendix P.

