- ¹³ Specimens indicated for Day 0 may be obtained within the 14 days prior to vaccination, except for a pregnancy test which must be performed on urine or blood specimens within 24 hours of vaccination with negative results received prior to vaccination.
- ¹⁴ Chlamydia/gonorrhea testing will only be performed for participants providing biopsy samples. In males, chlamydia/gonorrhea testing will be done on both rectal swabs and urine. In females, chlamydia/gonorrhea testing will be done on rectal swabs and on urine or vaginal swabs.
- ¹⁵ Trichomonas testing will be done with cervical/vaginal swabs or urine and will only be performed when clinically indicated for participants who agree to provide cervicovaginal secretion or vaginal biopsy samples.
- ¹⁶ Cervical/vaginal swabs for yeast and bacterial vaginosis testing will only be performed when clinically indicated for participants who agree to provide cervicovaginal secretion or vaginal biopsy samples
- ¹⁷ Antibody avidity, peptide microarray, metabolomic profiles, and proteomics assays may be done with serum collected for storage.
- y = SST blood collected for the Binding Ab and Neutralizing Ab assays will also cover specimen needs for the Fc-mediated Ab function assays; no separate blood draw is needed.
- z = Leukapheresis samples collected will cover specimen needs for the Ag-specific B-cell phenotyping, B-cell repertoire analysis and ICS assays; no separate blood draw is needed.

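### The innate Day 0 baseline may be drawn up to 14 days before vaccination, which costs precision in the Day 1, 3 and 7 change scores of participants drawn early

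*Protocol*

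**What the plan says.** **Timing of the baseline draw.** Appendix P attaches footnote 11 to the Visit 2 (Day 0) column: "Specimens indicated for Day 0 may be obtained within the 14 days prior to vaccination, except for a pregnancy test". Appendices L to O, which serve Part B only, carry the same rule; Appendix L reads "Specimens indicated for Day 0 may be obtained within the 14 days prior to vaccination", with the same single exemption. In Appendix P the block "Innate immunity and inflammation assays" schedules phenotyping (8.5 mL), RNA gene expression (3 mL) and serum cytokines/chemokines (5 mL) in the Day 0 column and again on Days 1, 3 and 7.

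**What the baseline is used for.**
- Section 5.3.2 (Part C), secondary endpoints 5: "Alterations in blood leukocyte populations during the innate response (day 1, 3 and 7) relative to prevaccine levels (day 0").
- Section 5.2.2 (Part B) uses the same reference: "Alterations of concentrations of immune cytokines and chemokines in serum samples postvaccination (days 1, 3, 7) relative to prevaccine levels (day 0").
- Section 6.4.4.1 plans repeated-measures models of "trajectories in innate immune responses over Days 1, 3, 7 relative to responses measured at Day 0".
- Section 10.3 says that, for three-dose groups, "primary timepoints for innate immunity and inflammation assays are baseline, and days 1, 3, and 7 post first vaccination".
- Secondary endpoint 6 in both parts compares cells, transcripts and soluble mediators at a reactogenicity visit with those on the day of the last vaccination.

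**Windows and exclusions.** Appendix W sets the Day 1 and Day 3 visits at -0/+0 days and Day 7 at -1/+1. Section 7.2, criterion 12, excludes "Any vaccines that are not live attenuated vaccines and were received within 14 days prior to first vaccination". Criteria 10, 11 and 13 use 30 days for live vaccines, ACAM2000 and three named adjuvanted vaccines.

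**Status.** The summary of this trial in Section 4.5, just before Section 4.5.5, reports that Part B enrolment is complete at 88 participants and that all have had at least two doses.

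**The concern.** The 14-day allowance suits baselines that move slowly, such as antibody or memory B cells. Blood cytokines, transcripts and activated leukocyte counts can move within days, which is why the protocol gives the Day 1 and Day 3 draws no tolerance. The value subtracted from all of those draws is the one left loose.

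The endpoint is a within-person change, so any error in the baseline passes directly into it. It also passes into the correlations with adaptive responses and the baseline-predictor analyses named in secondary objective 5. For a reaction after the first dose, the reference sample for endpoint 6 is the Day 0 sample, which under the footnote need not come from the day of vaccination.

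**Working it through.** **1. Does the footnote reach the innate tubes?** It is attached to Visit 2 and exempts only the pregnancy test. The three innate tubes are in that column: 8.5 + 3 + 5 = 16.5 mL. They are covered. At the second and third vaccinations (Visits 7 and 11) the same tubes are drawn at the vaccination visit, and no 14-day footnote applies there.

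**2. Interval from baseline to Day 1.** Drawn on Day 0: 1 - 0 = 1 day. Drawn on Day -14: 1 - (-14) = 15 days.

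**3. Another vaccine before the baseline.** The exclusions count back from the first study vaccination, not from the draw.
- Non-live vaccine on Day -15 (permitted), draw on Day -14: baseline 1 day after that vaccine, Day 1 sample 16 days after it.
- Non-live vaccine on Day -21, draw on Day -14: baseline 7 days after it.
- Live vaccine on Day -31 (permitted), draw on Day -14: baseline 17 days after it.

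Only a non-live vaccine just outside 14 days, combined with a draw near the start of the window, puts a recent vaccine response into the baseline.

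**4. Precision.** No figure in the protocol depends on the draw window. The nearest is Table 6-6 (one-sided 0.025 Wilcoxon test, SD 1). It reproduces by simulation with 20,000 runs: for a 1.0 SD difference, 80.0% against the stated 81% (n = 18) and 77.9% against 78% (n = 17).

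For a change score, SD of change = SD × sqrt(2(1 - rho)), where rho is the correlation of baseline with the post-vaccination value. The protocol gives no rho, so the range below is an assumption. It uses n = 18 per arm and the same test; the differences are in cross-sectional SDs.

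| rho | SD of change | Power, 0.6 SD difference | Power, 1.0 SD difference |
|---|---|---|---|
| 0.9 | 0.447 | 96.4% | 100% |
| 0.8 | 0.632 | 76.5% | 99.3% |
| 0.7 | 0.775 | 58.3% | 95.0% |
| 0.6 | 0.894 | 47.5% | 88.3% |
| 0.5 | 1.000 | 38.8% | 80.3% |
| 0.3 | 1.183 | 29.5% | 65.5% |

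The table shows sensitivity to rho, not the loss in this trial. If a share f is drawn early with correlation rho1 and the rest have rho0, the variance of change is 2[1 - (1 - f)rho0 - f rho1]. With rho0 = 0.8 and rho1 = 0.7, f = 0.1 gives 0.42 (SD 0.648) and f = 0.5 gives 0.50 (SD 0.707), against 0.632 with no early draws. If an early draw does not lower rho, nothing is lost.

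**5. One bad baseline in Part C.** With 10 vaccinees per arm (Section 6.1.4), an error e in one participant's baseline moves the arm's mean change by e/10.

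**The case against.** The footnote is permissive. The schedule places these tubes at Visit 2, and how often sites draw early is unknown; Section 10.1 leaves collection guidance to site instructions that are not part of the protocol. Part B is fully enrolled and past its first doses, so editing Appendices L to O would change nothing. Section 9.3 requires vital signs, a symptom-directed evaluation and an intercurrent-illness check before each injection. Section 7.4.1 lists symptoms that could mask a vaccine reaction as a factor in delaying vaccination. Other vaccinations are recorded as concomitant medications, so a recent one can be found. All of this stands and limits the point. What it does not remove is the gap itself: those checks are tied to the vaccination visit, and nothing in the protocol applies them, or the other-vaccine interval, to an early draw.

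A reader might infer three stronger things that the protocol does not support:
- **Biased adjuvant comparisons in Part B.** The arms are randomised and blinded under one footnote, so the cost there is precision.
- **Another vaccine's response routinely in the baseline, able to mask or reverse the adjuvant signal.** This needs the edge case in step 3, and one such participant moves a Part C arm mean by a tenth of the error.
- **A difference between Groups 7 and 8 from drawing practice.** They enrol one after the other, so randomisation would not balance a change in practice, but nothing shows that practice changed.

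**Conclusion.** The point holds as a gap in timing control for a secondary endpoint. The innate reference sample may be up to 14 days old at vaccination, while the Day 1 and Day 3 samples compared with it have no tolerance. For participants drawn early, up to two weeks of unrelated within-person variation enters the change score, and for a first-dose reaction the endpoint 6 reference may not come from the day the endpoint names.

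The main consequence is lost precision. Its size cannot be stated, because the protocol gives neither the within-person correlation over 1 and 15 days nor the share drawn early; the power figures above rest on assumed correlations. No safety or primary endpoint is affected. The change is worth making for Part C because it is cheap.

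**What to change.** **Part C.** Amend Appendix P footnote 11 to add a second exception: the phenotyping, RNA gene expression and serum cytokine/chemokine tubes must be drawn on the day of vaccination, before injection. Keep the 14-day allowance for every other Day 0 specimen.

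**Part B, and any Part C participants already drawn early.** Identify the innate baselines not drawn on the day of vaccination, report how many there are by arm, and run the innate change analysis with and without them as a sensitivity analysis.

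**Cost.** One footnote and some loss of scheduling flexibility. The 16.5 mL is already in the Day 0 volume, and the highest 56-day total in Appendix P is 478 mL against the 500 mL limit in Section 10.2, so no blood is added. Visit 2 has no safety bloods and the pregnancy test can be done on urine, so a participant who pre-draws the other specimens may need one additional venipuncture on vaccination day.
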